FIOC was designed specifically to aid development of positive coparenting alliances between at-risk (unmarried, uncoupled, low income) African American mothers and fathers having a first baby together. In the RCT, randomly-assigned control group families (referred by already-known referral agents and partners who worked closely with our team on the pilot projects) will receive Pinellas County services as-usual for pregnant parents and assistance of a Resource and Referral Navigator for referrals to desired community services ("Treatment as Usual", or TAU). The remaining (experimental group) families will receive the same services and aid, plus the 6-session FIOC prenatal intervention with a post-natal booster session. The first 150 families consented in will be assigned to groups via urn randomization. The remaining families recruited up to 170 will be assigned to the experimental (FIOC) group to achieve balance in the number of families contributing postnatal follow-up data longitudinally in the two groups to allow minimally sufficient statistical power for analyses. The FIOC intervention addresses the importance of safe, healthy families for early infant development, the impact a cooperative and sustained coparenting alliance can have in promoting positive infant development, challenges unmarried parents face cultivating a coparenting alliance together when their commitment to one another as romantic or married partners is in doubt, and ways to surmount these obstacles, maintain rapport, and sustain a strong alliance.

All 170 participating families, both at intake (prior to the intervention) and then again at 3 and 12 months post-partum, will report beliefs about fatherhood; extent of depressive symptomatology; and quality of the mother-father partnership. State-of-the-field coparenting observations will be conducted at each follow-up, along with measures of parental stress, intimate partner violence (IPV), perceived coparenting support, father engagement, and infant socioemotional adjustment. Analyses will examine impact of the intervention on promoting more supportive, coordinated post-partum coparenting alliances and more positive adult and infant outcomes. Exploratory analyses will examine links between father involvement and child adjustment and whether this coparenting intervention also stands to prevent IPV.

2. Background information

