Child Outcome Measures at Time 3: An adapted version of the Infant Toddler Social Emotional Assessment (ITSEA; Carter & Briggs-Gowan, 2006), comprised of the full Brief Infant Toddler Social Emotional Assessment (BITSEA) and select additional scale items from the longer ITSEA instrument, was developed in consultation with the scale’s author. The instrument measures both social-emotional/ behavioral problems and delays in competency for children ages 12-36 months. It is a 71-item parent-report index constituting of six sub-scales: Problem behavior, competence, compliance, negative emotionality, aggression, and sleep.

5. Sample size justification:

We employed a computer program provided by Murphy et al. (2009; the same information is available from the tables in Cohen, 1988) to compute the significance level required for a projected sample size, incorporating attrition estimates, of $N=120$ (60 each in the treatment and control groups, respectively). Assuming the null effect hypothesis and alpha set at .05 and power of .8, an $F(1, 117)$ of 7.74 with a $d = .514$ is required for significance. Keeping the null hypothesis test, alpha .05 and lowering power to .5, an $F(1, 117) = 4.03$ with a $d = .37$ is required for significance. Drawing on effect size estimates from the feasibility study, even with low power (.5) resulting in a $d=.37$ we would be positioned to establish the effect of the FIOC treatment for 10 of the 12 FIOC variables (10 of the 12 SCID-evaluated couple problem-solving and communication variables summarized earlier had a d greater than .33).

6. Sample type or inclusion and exclusion criteria for participating in the research:

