An important aspect of this work is carefully monitoring the experiences of the enrolled families. The entire project team will be involved in this endeavor, but major responsibilities for connecting with families will be shouldered by the Recruiter/Intake Coordinator. Her role involves talking with parents who have signaled their interest and enrolling them in the study. Each week's recruitment, enrollment and retention activities are reviewed by the project operations team, and appropriate strategies for improvement are identified and implemented. Retention of parents who have been randomized to the control condition is always of special concern; in this project, retention of control group parents is promoted by episodic contacts with the assigned Resource and Referral Navigator, a Congratulations card after the baby is born, and episodic staged reminder texts and newsletters. Retention of parents who have been randomized to the intervention condition is likewise supported by a R&R Navigator, and Mentors are also important to retention efforts with intervention group families. All families will be contacted by female Resource and Referral Navigator and mentors throughout the study duration as is needed for scheduling, follow-ups on missed appointments, formal check-ins at 1 and 9 months postpartum, and planning for 3- and 12-month post-partum follow-up visits. When deemed necessary to ensure retention, fathers will be contacted for the above purposes by male staff members. **In addition, families will be contacted more frequently (at least once-monthly) during periods of elevated local or national stress or unrest to ensure any emergent, unforeseen needs they may have for new resources get addressed.** Should challenging issues arise, Clinical Supervisors, kept informed of family situations by project Mentors during weekly supervision meetings, help guide Mentors in responding to clinical challenges and monitor potential adverse effects in an ongoing way during supervision meetings. Monitoring can also occur at any time and with any required frequency in the event a situation qualifying as an adverse event occurs in between weekly supervision meetings. If clinically concerning scenarios of any sort arise, the Mentors first attempt to resolve the situation through consultation with clinical supervisors, who in turn report weekly (and more often if needed) to the PI and Co-PI. If resolution of a clinically-concerning scenario cannot be reached through use of supervision and rises to the level of an adverse event, the clinical team (co-PI and clinical supervisor informed by the Mentors) and PI coalesce to form a plan that is then reported to the project's Data and Safety Monitoring Board, who comment on the plan and provide guidance. Expert consultant [name] can also be available to consult as needed on cases requiring additional expert input. Families will be retained in the project so long as they continue to express interest in participation and can continue to be safely enrolled. If a family must be withdrawn from the project based on assessments of concerns around safety, unresolved trauma, or other level of psychological or medical need beyond that which the project can safely provide, appropriate community resources and referrals are provided to the parents.

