Threats of danger to others include disclosure of potential physical harm by a participant to others, including members of the participant's family or other individuals in the community. Mentors will report such disclosures to the Co-PI and Clinical Supervisor. These disclosures will be handled in accordance with Florida law, requiring reporting to proper legal authorities by project staff.

4. Family crisis

Family crisis involves a range of situations that threaten the ability of subjects to provide essential supports for their children. Mentors will provide appropriate referrals to assist parents with relieving crisis situations.

5. Domestic Violence

A coordinated response to disclosures of domestic violence will be initiated, tailored to the particular issues disclosed during the intervention. All staff who work with families have been trained on the project's safety plans, and how to assist the mother in taking actions she has deemed appropriate to increase her safety. Plans can include, but not be limited to, project-specific safety planning, working with CASA (Community Action Stops Abuse, [name]), the local certified domestic violence center, taking steps to go into shelter, contacting law enforcement, obtaining an Injunction for Protection, and/or terminating participation in the project. The project safety plan is included as a separate document.

5. Reporting procedures for adverse events

Potential adverse events during assessments/intervention are limited to those described above and will be addressed in a timely manner by the Mentors, Co-PI, Clinical Supervisor and P.I. *Reporting Procedure for Serious Unanticipated Adverse Events*. In the event of any unanticipated serious adverse event, the P.I. will ensure that the event is reported to the proper authorities within 24 hours by phone, fax, and/or email and will submit a written report to the Program Official no more than two days later. The project staff will also utilize the following reporting procedures:

1. When project staff and/or the P.I. become aware of a serious adverse event, reporting requirements must be implemented in a timely manner.
2. The P.I. will complete an "Adverse Event Reporting Form" and submit the form to the University of South Florida IRB Officer.
3. The IRB Officer immediately distributes the form to USF IRB Officials.

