## **Cover Letter**

### **Statistical Analysis Plan**

**Document Date 1.31.2022**

**NCT03097991**

### **FIOC Statistical Analysis Plan**

- Initial descriptive summations and simple statistical tests will compare groups.

- Primary Aims 1-4: Effects of the intervention. To examine if coparenting and individual adjustment outcomes are superior for FIOC families than for control group families at 3- and 12-months post-partum two-sided independent sample t-test for equivalence will first be employed for single time point comparisons. We will test hypotheses further using linear or generalized linear models to control for potential confounding and account for imbalance between the two treatment conditions.
- For longitudinal outcomes that are continuous (measured at Baseline; 3; and 12 months post-partum) we will use repeated measures analysis of covariance (ANCOVA; Crowder & Hand, 1990) to detect if treatment and control groups perform differently at any time points. For longitudinal outcomes that are categorical, generalized linear model (GLM, McCullagh & Nelder, 1989) will be used for the same purpose. Repeated measures ANCOVA and GLM allow us to account for correlation between repeated measures and detect possible moderating/confounding between treatment effects and subject individual differences. Multiple comparison adjustment will be addressed in analyses. We will report significance under both regular (.05) and Bonferroni-adjusted alpha.
- Exploratory Aim 1: To examine whether extent of father engagement is associated with better infant socioemotional adjustment regression analyses will examine variance in infants' 12-month ITSEA Internalizing, Externalizing, Dysregulation and Competence scores explained by 3- and 12-month father engagement.
- Exploratory Aim 2: To examine whether FIOC prevents the emergence of IPV and help to prevent future IPV in couples where it was previously reported, we will first explore simple chi-square analysis to compare FIOC and TAU conditions on the binary variable of any instance of physical violence between partners reported on the CTS2 over the 12 months of follow-up. Next,

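### Withdrawal for safety or IPV can remove the IPV outcome itself, and the SAP does not say how withdrawn families enter the FIOC v TAU comparison

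*Protocol*

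**What the plan says.** **Withdrawal.** Protocol section 13, item 1 (monitoring of recruitment, enrollment and retention), keeps families in the project while they remain interested and can safely stay. It then covers what is offered "If a family must be withdrawn from the project based on assessments of concerns around safety", or for unresolved trauma or other needs beyond the project's capacity. Section 13, item 4 (Domestic Violence), lists "terminating participation in the project" as one of several elements that a safety plan may contain. Neither place says whether a withdrawn family still gives follow-up data.

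**IPV analysis.** Under Exploratory Aim 2 the SAP plans three steps:
- a chi-square comparing FIOC and TAU on "any instance of physical violence between partners reported on the CTS2" during the 12 months of follow-up;
- a linear regression of the 12-month CTS2 score on group and baseline score;
- a hierarchical regression of IPV severity over follow-up.

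The SAP names no analysis population, no missing-data method and no rule for withdrawn families.

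**Contrast.** Hypothesis 8 (protocol section 3) compares TAU families with those who complete FIOC.

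**Contact by arm.** Sections 1 and 4 give FIOC families mentors, two individual sessions, six prenatal sessions and a postnatal booster. TAU families have the Resource and Referral Navigator. Assessors see both arms.

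**The concern.** The event being counted is also a reason for the count to be missing. A couple whose violence comes to light may leave before a postnatal CTS2 is taken, and an analysis of CTS2 reports then has no record of that violence. If this happens equally in both arms, both observed rates fall but the odds ratio is preserved. If it happens more in one arm, that arm looks safer than it is.

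There are two reasons to expect heavier loss in FIOC. Mentors meet those couples repeatedly, and the escalation route in section 13, item 1 runs through mentors and their weekly supervision. Read literally, Hypothesis 8 also removes non-completers, safety withdrawals included, from FIOC only. At stake is a conclusion that a coparenting programme prevents partner violence. The aim is exploratory, but readers would act on such a statement.

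**Working it through.** **1. The plan's own figures.** The only power statement (protocol section 5) concerns coparenting outcomes, not IPV. It uses "alpha set at .05 and power of .8" with N = 120 ("60 each in the treatment and control groups, respectively") and states "an $F(1, 117)$ of 7.74 with a $d = .514$ is required for significance". Converting, d = 2√(F/117) = 2√(7.74/117) = 0.514, and the noncentral F with 1 and 117 df gives power 0.797 at that d. The figure reproduces. I take only the 60 per arm from it. That number is already net of attrition, so using it as the size before safety withdrawal is a simplification.

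**2. Inputs that the documents do not give.** They state no IPV rate and no withdrawal rate. I assume a true IPV rate p of 20%, 30% or 40%, equal in both arms (no treatment effect). A share wF of affected FIOC families and wC of affected TAU families is lost before any postnatal CTS2, and unaffected families all stay.

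**3. Formula.** Among the families that remain,

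- observed rate = p(1 − w)/(1 − pw);
- observed odds = p(1 − w)/(1 − p);
- observed odds ratio, FIOC v TAU = (1 − wF)/(1 − wC), whatever the value of p.

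**4. One case by hand.** Take p = 30%, 60 per arm, wF = 30%, wC = 0. Each arm has 18 affected and 42 unaffected families. FIOC loses 0.30 × 18 = 5.4, leaving 12.6 of 54.6, or 23.1%. TAU shows 18 of 60, or 30.0%. The odds ratio is (12.6/42)/(18/42) = 0.70.

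**5. Range.** Observed rates below are for p = 30%. The last column is the chance that a two-sided 5% Pearson chi-square rejects although there is no effect, by exact enumeration with arm sizes rounded to whole families, for p = 20% / 30% / 40%.

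| wF | wC | FIOC observed | TAU observed | OR | Rejection (%) |
|---|---|---|---|---|---|
| 0 | 0 | 30.0% | 30.0% | 1.00 | 5.0 / 5.2 / 5.1 |
| 10% | 0 | 27.8% | 30.0% | 0.90 | 5.7 / 5.7 / 6.0 |
| 20% | 0 | 25.5% | 30.0% | 0.80 | 7.7 / 8.5 / 8.9 |
| 30% | 0 | 23.1% | 30.0% | 0.70 | 11.2 / 13.6 / 15.0 |
| 50% | 0 | 17.6% | 30.0% | 0.50 | 24.8 / 32.8 / 39.0 |
| 30% | 15% | 23.1% | 26.7% | 0.82 | 6.9 / 7.3 / 7.8 |
| 30% | 30% | 23.1% | 23.1% | 1.00 | 5.0 / 5.1 / 5.2 |

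With 30% or 50% FIOC-only loss, nearly all rejections favour FIOC. What matters is the difference in loss between arms, not the total.

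**6. Counting withdrawal as an event.** This returns the odds ratio to 1 only if withdrawn families truly had the outcome and violence is found equally well in both arms. Heavier detection in FIOC breaks the second condition.

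**The case against.** Several points on the other side stand.

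- **Exclusion is not stated.** A reader might infer that withdrawn families are dropped from the IPV analysis. No text says so; the documents are silent. A family withdrawn after the 3-month visit already has a postnatal CTS2 that the chi-square could use. This has limits: six of the seven joint FIOC sessions are prenatal, so a withdrawal they prompt comes before any postnatal CTS2, and the second SAP model needs the 12-month score in any case.
- **Withdrawal does not follow automatically from IPV.** Ending participation is one option in a list, and section 13, item 3 describes higher-conflict couples continuing with extra preparation. Families with serious IPV are excluded before randomisation, which makes very high loss among affected families less likely.
- **Detection is not confined to FIOC.** A reader might infer this from the mentor sessions. But the Navigator serves both arms, and assessors, who see both, are trained on the Safety Protocol. One sentence in section 13, item 1 says that all families are contacted by the Navigator and mentors. It should be reconciled with section 4, which introduces mentors to the treatment group.
- **The direction is not certain.** Section 13, item 1 also credits mentors with helping FIOC retention, which works against net loss there.
- **A composite endpoint has its own bias.** As the main analysis it would change the outcome from physical violence to something wider, score some prenatal withdrawals as first-year events, and could turn the bias against FIOC. That is a good reason to keep it as a sensitivity analysis.

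**Conclusion.** The plan leaves outcome-dependent loss in the exploratory IPV comparison with no rule for handling it, and the completer wording of Hypothesis 8 makes that worse. Bias towards FIOC is probable rather than established. Its size depends wholly on unequal loss of affected families, for which the documents give no figure. A small imbalance does little: 10% FIOC-only loss gives an odds ratio of 0.90 and about 6% false rejection. At 30% FIOC-only loss the odds ratio is 0.70 and false rejection is 11% to 15%; at 50% these are 0.50 and 25% to 39%. If TAU loses half the share that FIOC does (30% v 15%), they are 0.82 and 7% to 8%. Equal loss leaves no bias in the odds ratio.

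A reader might go further and call any favourable IPV result an artefact. The documents do not support that: they show a route to bias, not its occurrence. Nor does this point directly touch the primary aims.

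**What to change.** On the analysis side only, Exploratory Aim 2 of the SAP should:

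1. **Compare all randomised families as assigned**, not FIOC completers, and use any postnatal CTS2 obtained before withdrawal. By section 1, "The first 150 families consented in will be assigned to groups via urn randomization", so the randomised set is those 150. The SAP should say separately where the up to 20 later families (170 − 150) placed in FIOC without randomisation belong.
2. **Report withdrawals for safety or IPV by arm**, with reason and timing. No text says that reasons are recorded, so the sponsor should confirm this.
3. **Keep the CTS2-based comparison as the main exploratory analysis and prespecify a sensitivity analysis** that counts withdrawal for IPV or partner-safety concerns as an event. Claim a preventive effect only if the two agree.

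The cost is SAP wording, one table and one further analysis. The downside is that some withdrawals will not reflect physical violence in the child's first year, and heavier detection in FIOC may make the sensitivity analysis err against FIOC. That is why the two results should be read together. No change to any withdrawal or safety procedure is proposed.

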Appendix A
Community Recruitment Activities (Scope of Work)
Completed by Community Development & Training Center (CDAT)
During Fall/Winter 2019-20
Responsive to Specific Aim 7 of USF's NIH-sponsored FIOC project

Community Development & Training Center (CDAT) will lead a collaborative media and marketing campaign to reach potential participants for the University of South Florida's NIH-supported "Figuring it Out for the Child" (USF FIOC) Program. The campaign will leverage the marketing reach and organizing capacity of several partner organizations, combined with the USF FIOC network of existing community contacts, to implement a comprehensive approach. Media partners to the campaign will include the following:

- The New Image Project
- Tampa Bay Breakfast Club
- The Power Broker magazine
- TheBurgVotes.com
- The Weekly Challenger Newspaper
- The Bulletin Newspaper
- On the Beat St. Pete
- 96.3 FM (radio)
- 99.1 FM (radio)

The campaign's scope of work will include the following:

- CDAT's production of creative content including graphic designs (infographics, memes, and advertisements) and video interviews with parents who participated in the FIOC program and expressed their satisfaction with the program and their openness to being recontacted.
- Print ad placements
- Digital ad placements
- Social media ad placements
- On-air radio interviews and special programs
- Facebook Live interviews and special programs
- Print & digital articles (shared via social media)
- Outreach for and facilitation of a Final Push Luncheon with Key Partners (targeting attendance by 50 partners and prospective partners and 4 media outlets)

The campaign will operate from October 23, 2019 through March 1, 2020. New graphic content generated will be submitted for approval by Amendment through USF's Internal review Board. The goal of the campaign is to generate as many as 65 new in-bound inquiries from prospective participants and for the inquiries to result in 20-25 new participants to help complete enrollment in the NIH-sponsored FIOC program.

## **Cover Letter**

### **Statistical Analysis Plan**

**Document Date 1.31.2022**

**NCT03097991**

### **FIOC Statistical Analysis Plan**

- Initial descriptive summations and simple statistical tests will compare groups.

- Primary Aims 1-4: Effects of the intervention. To examine if coparenting and individual adjustment outcomes are superior for FIOC families than for control group families at 3- and 12-months post-partum two-sided independent sample t-test for equivalence will first be employed for single time point comparisons. We will test hypotheses further using linear or generalized linear models to control for potential confounding and account for imbalance between the two treatment conditions.
- For longitudinal outcomes that are continuous (measured at Baseline; 3; and 12 months post-partum) we will use repeated measures analysis of covariance (ANCOVA; Crowder & Hand, 1990) to detect if treatment and control groups perform differently at any time points. For longitudinal outcomes that are categorical, generalized linear model (GLM, McCullagh & Nelder, 1989) will be used for the same purpose. Repeated measures ANCOVA and GLM allow us to account for correlation between repeated measures and detect possible moderating/confounding between treatment effects and subject individual differences. Multiple comparison adjustment will be addressed in analyses. We will report significance under both regular (.05) and Bonferroni-adjusted alpha.
- Exploratory Aim 1: To examine whether extent of father engagement is associated with better infant socioemotional adjustment regression analyses will examine variance in infants' 12-month ITSEA Internalizing, Externalizing, Dysregulation and Competence scores explained by 3- and 12-month father engagement.
- Exploratory Aim 2: To examine whether FIOC prevents the emergence of IPV and help to prevent future IPV in couples where it was previously reported, we will first explore simple chi-square analysis to compare FIOC and TAU conditions on the binary variable of any instance of physical violence between partners reported on the CTS2 over the 12 months of follow-up. Next,

we will conduct a linear regression model with intervention group and baseline CTS2 scores as predictors and CTS2 12-month scores as outcome variables. Next, hierarchical regression will be used to assess the main effects of the intervention group and severity of previous violence (reported on the CTS2 at baseline) on the severity of IPV over the 12 months of follow-up, and the interaction effect of FIOC x previous IPV on IPV severity at follow-up.
